### **13.3. Procedures for Reporting Adverse Events**

Subjects will be instructed to inform clinic personnel of the AEs that may arise during the course of the study. Treatment of any AEs will be administered under the direction of the Investigator.

All symptoms will be recorded by clinic staff and will be reviewed by the Investigator or Sub-Investigators prior to any subsequent dosing.

When appropriate, medical tests and examinations will be performed to document resolution of the event(s).

---

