## Experimental Design

This is a single-center, open label safety and tolerability trial. Approximately sixteen (16) individuals with C9orf72 amyotrophic lateral sclerosis (ALS) will be enrolled. Subjects will be screened to determine eligibility according to the specified inclusion/exclusion criteria. Following informed consent, screening, and enrollment, during study visit 1, subjects will undergo clinical examinations and questionnaires including the validated amyotrophic lateral sclerosis functional rating scale-revised (ALSFRS-R). Subjects will have blood work performed to monitor clinical safety, RAN proteins and biomarker analyses. Lumbar punctures will be performed to allow measurements of RAN protein levels in the cerebrospinal fluid (CSF) and for molecular and biomarker analyses. MRI/DTI imaging will be obtained at the beginning of the study and at the end of the drug treatment phase. Subjects will return on Day 1 for swallowing and respiratory evaluation. The subjects will then be given a first dose of Metformin (with escalating dose of the drug. The initial dose during week one will begin at 500mg/day, in the following weeks this will increase to 1000 mg/day (week two), 1500 mg/day (week three) and 2000mg per day (weeks 4 to 24). The subjects will begin by taking the first dose in the morning during week one and then morning and evening doses in weeks 2-24 with an interim assessment at days 42, 84 and final evaluation at 168 days (+/- ~7) to assess the safety and tolerability of Metformin.

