## 8. STUDY DESIGN

Approximately 16 subjects with C9orf72 positive ALS will be enrolled. The subjects will be instructed in the use of Metformin and receive the first dose of Metformin under supervision of [name] during Visit 1.

Subjects will then continue on Metformin per the dosing schedule for 24 weeks; with interim safety assessments at days 42, 84, 126 and 168 (+/- ~7 days).

Subjects will be screened to determine eligibility according to the specified inclusion/exclusion criteria.

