### **11.3. Subject Compliance**

Subject compliance will be assessed at all visits with direct and open questioning about compliance and adverse events. All returned medication will be counted. Greater than 10% noncompliance will prompt re-education of subject by the investigator on the importance of medication compliance.

---

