## 12.2. Timing of Study Activities

No study procedures will be performed prior to the signing of the Informed Consent Form (ICF). All subjects will sign an ICF prior to undergoing any study tests or procedures.

Visit windows are consecutive calendar days and the target visit dates are calculated from the Baseline Visit, which should occur within 14 to 28 days of the Screening Visit. All clinic visits and calls after the Baseline visit will have a +/- 7 work day window.

Inclusion in the study is entirely voluntary and subjects may withdraw at any time for any reason. Possible reasons for withdrawal could include serious adverse events, adverse events, and subject's choice. Subjects wishing to stop medication will immediately discontinue test article. Subjects who elect to discontinue medication will be asked to comply with end of study assessments (visit 4 on Table 3 Schedule of Activities) at a follow up visit in an outpatient setting (to be determined by Investigator or Staff) at 14 +/- days after the last treatment dose. Subjects who withdraw due to an adverse event will be followed whenever possible until resolution of the adverse event. It may be appropriate for the subject to return to the site 2 weeks after the subject is off study to evaluate for resolution of any adverse events and to receive further information about options for future clinical care. The Investigator will decide the course of action.

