As part of the screening visit, the investigator will determine the competence of caregiver to administer the study drug at home. Teaching will begin on the importance of compliance and proper handling of study drug. All inclusion and exclusion criteria and safety laboratory tests will be reviewed by the investigator prior to scheduling the baseline visit (visit 1 on schedule of activities table). A paper log will be kept at the site to record all subjects screened for entry into the study. This information will also be captured electronically in the electronic data capture system (EDC) using REDCap. REDCap (Research Electronic Data Capture) is a secure, Web-based application designed to support traditional case report form data capture. Demographic characteristics of all subjects who are screened will be recorded whether or not they qualify for entry into the study. The reason for non-qualification will be recorded for all subjects who are not eligible. The reason for nonparticipation will also be recorded for subjects who are eligible but choose not to participate in the trial. If a subject fails screening for the study, the subject can be re-screened if the investigator determines it is appropriate to do so. At any time during the study, repeat laboratory tests can be obtained if the investigator or central laboratory believes that a laboratory test result is in error. Additional laboratory tests may also be obtained at any time during the study, at the discretion of the investigator.

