### **13. SAFETY AND ADVERSE EVENTS**

The AE definitions and reporting procedures provided in this protocol comply with all applicable International Conference on Harmonization (ICH) guidelines. Study staff will carefully monitor each subject throughout the study for possible AEs. All AEs will be documented on CRFs designed specifically for this purpose. It is also important to report all AEs, especially those that result in permanent discontinuation of the investigational product being studied, whether serious or non-serious.

**Safety Review Plan and Monitoring-** Oversight of participant safety includes review of adverse events as well as study progress, data integrity and study outcomes. The study will engage a physician safety monitor to discuss issues regarding side effects and adverse events. The safety monitor is external to the clinical study and is free of any conflicts of interest to maintain independence and objectivity.

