### **13.1. Adverse Event Reporting and Follow Up**

Subjects will be instructed to inform clinic personnel of any untoward medical symptoms and/or events that may arise during the course of the study. If an adverse event is experienced by a subject, then the subject will be questioned concerning symptoms that may have occurred after the administration of the study drug. The incidence, severity and duration of all AEs will be recorded according to the following scale:

Mild	Adverse event resulting in discomfort, but not sufficient to cause interference in normal daily activities
Moderate	Adverse event resulting in discomfort that is sufficient to cause interference in daily activities.
Severe	Adverse event resulting in discomfort causing an inability to carry out normal daily activities

Subjects who withdraw due to an adverse event will be followed whenever possible until resolution of the adverse event. It may be appropriate for the subject to return to the site 2 weeks after the subject is off study to evaluate for resolution of any adverse events and to receive further information about options for future clinical care. The Investigator will decide the course of action.

---

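### No adverse event inquiry is scheduled between Visit 1 Day 2 and Visit 2, although the dose rises three times at home in that period with no tolerability condition

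*Combined protocol and SAP*

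**What the plan says.** The Synopsis (Experimental Design) starts subjects on 500 mg/day in week 1 and then gives "1000 mg/day (week two), 1500 mg/day (week three) and 2000mg per day (weeks 4 to 24". Table 2 and section 11.1 repeat the weekly 500 mg steps, and none of the three places attaches a condition to a step. The first dose is supervised at Visit 1 (section 8). Later doses are taken at home: under section 12.2.1, "the investigator will determine the competence of caregiver to administer the study drug at home".

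Section 13.3 sets the safeguard: "All symptoms will be recorded by clinic staff and will be reviewed by the Investigator or Sub-Investigators prior to any subsequent dosing". How symptoms come to staff's attention is described in three places:

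- Section 11.3: "Subject compliance will be assessed at all visits with direct and open questioning about compliance and adverse events".
- Section 13.1: subjects are told to report symptoms, and "If an adverse event is experienced by a subject, then the subject will be questioned concerning symptoms".
- Section 13: "Study staff will carefully monitor each subject throughout the study for possible AEs".

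In Table 3 the AE row is marked at Visit 1 Day 2 and next at Visit 2 (6 weeks). Section 8 likewise has subjects continue on metformin "with interim safety assessments at days 42, 84, 126 and 168 (+/- ~7 days". The first scheduled phone call is at week 18 (12.2.2.4).

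**The concern.** The plan states a review requirement but schedules no contact during titration to feed it. Direct AE questioning happens at visits, and there is no visit while the dose is rising. A subject whose symptoms are not volunteered moves up to 2000 mg/day without being asked about them.

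This matters because safety and tolerability are the primary objective, summarised by type, incidence and severity of AEs. Section 13.3 also wants onset time and duration for each event, and the causality scale in 13.2 relies on timing relative to dosing. A symptom first asked about at Visit 2 has to be placed from memory over several weeks and four dose levels. With about 16 subjects, one subject wrongly counted moves an incidence by 1/16 = 6.25 percentage points. Mild and moderate events and their onset are the most exposed. Permanent discontinuations are not at issue, because section 12.2.2.8 requires them to be documented within 24 hours.

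**Working it through.** This is calendar arithmetic; no power formula applies.

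**Inputs.** Weekly 500 mg steps up to 2000 mg/day from week 4 (Synopsis, Table 2, 11.1). First dose at Visit 1 (section 8), taken as day 1. Visit 2 at week 6 +/- 3 days (12.2.2.2). Two other windows also appear: about 7 days (section 8), and in section 12.2, "All clinic visits and calls after the Baseline visit will have a +/- 7 work day window". About 16 subjects (section 8), of whom 3 were already enrolled when the COVID-19 text was written (12.2.2.5).

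**The plan's own figure.** 6 x 7 = 42 days, as stated.

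**Step days.** 1 + 7k for k = 1, 2, 3 gives days 8, 15 and 22. If visit days are counted from Visit 1 Day 1 and the first dose is on Day 2, they become 9, 16 and 23.

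**Visit 2 against the steps.** Days at 2000 mg/day before Visit 2 = Visit 2 day - 22. Delay for a symptom starting on day 1 = Visit 2 day - 1. Seven work days span 9 to 11 calendar days depending on the weekday; 11 is used.

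| Window | Visit 2 day | Days after reaching 2000 mg/day | Days since a day 1 symptom |
|---|---|---|---|
| Nominal | 42 | 20 | 41 |
| +/- 3 days (12.2.2.2) | 39 to 45 | 17 to 23 | 38 to 44 |
| +/- about 7 days (section 8) | 35 to 49 | 13 to 27 | 34 to 48 |
| +/- 7 work days (12.2) | 31 to 53 | 9 to 31 | 30 to 52 |

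The visit-specific row is the one to rely on. The wider rows only show that the order does not depend on the window: the earliest Visit 2, day 31, is still after day 22 or 23.

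**What calls would change.** Calls on days 7, 14 and 21 put an inquiry before 3 of 3 increases, but they leave 42 - 22 = 20 days at the top dose with none. A call on day 28 comes 28 - 22 = 6 days after the top dose starts and leaves 42 - 28 = 14 days to Visit 2.

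**Why the calls need their own window.** Under the 7 work day rule a day 7 call could slip to day 7 + 9 = 16 or 7 + 11 = 18, past the steps on days 8 and 15.

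**Load.** 4 x 16 = 64 calls, or 4 x (16 - 3) = 52 if the 3 subjects already enrolled are past titration.

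**The case against.** The best defence is that the protocol already has safeguards. Subjects are told to report any untoward symptom, staff undertake to monitor throughout, nothing forbids unscheduled contact, and section 14 allows stopping or suspension on a treating physician's recommendation. Tablets are counted at Visit 2, so substantial missed dosing could show up. Metformin is described as widely used and well tolerated, no formal tests are planned on the safety endpoints, and symptoms nobody volunteers are likely to be the milder ones.

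Much of this stands, and it limits the point. A reader might infer that the 13.3 review can reach nothing but volunteered symptoms, or that subjects go unmonitored during titration. The documents do not support that: section 13 promises monitoring and leaves room for ad hoc contact. What they show is that no active inquiry is scheduled. A reader might also infer that calls before the three steps would settle the matter; the working shows that they leave the first weeks at 2000 mg/day uncovered. Nor can the 6% who discontinued for diarrhea (section 6.4) be used to size the loss, since it counts discontinuations and not unvolunteered symptoms.

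Section 9.2.1 admits subjects who take or have taken metformin, and section 9.2 collects pretreatment AEs from current users. For current users the concern may be smaller.

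What the defence does not supply is any dated contact between Visit 1 Day 2 and Visit 2, or any condition on a dose step.

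**Conclusion.** The point holds as a cheap improvement to the conduct of the study. It does not show that the titration is unsafe. All 3 increases come before the first scheduled AE inquiry after Visit 1, under every window in the protocol. By the Visit 2 window that inquiry comes 17 to 23 days after the top dose is reached, and 38 to 44 days after a symptom that began on day 1. Until then the 13.3 review depends on subjects speaking up and on contact that the plan does not schedule.

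Two assumptions are needed: the first dose is day 1, and the timeline under section 12.1, which is not shown in the text, adds no contact. The second is plausible because section 8, Table 3 and the visit-by-visit text all lack one. The documents give no rate of unvolunteered symptoms, so the number missed cannot be estimated.

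**What to change.** Add four brief AE phone calls by the existing coordinators to Table 3: days 7, 14 and 21, each made within the 2 days before the step, and one about a week after 2000 mg/day is reached (about day 28). Exempt them from the 7 work day window in section 12.2. AE review by phone is already used at weeks 18, 36 and 52.

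State that the dose is not increased until the call has been made and the investigator has reviewed any symptoms reported. Leave the existing 13.3 sentence on review before subsequent dosing as it is. A rule that merely let a symptomatic subject continue at the current dose pending review would be looser than that sentence.

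The cost is 4 calls per subject, at most 64 for 16 subjects (52 if the 3 already enrolled are past titration), a protocol amendment, and a delay in reaching 2000 mg/day for any subject whose step is held.

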#### **CONFIDENTIAL INFORMATION**

The information in this study protocol is confidential. Any disclosure, copying or distribution of the information contained within is strictly prohibited without written consent from University of Florida.

Adverse events will be coded into the Preferred Term (PT), classified according to the current version of Medical Dictionary for Regulatory Activities (MedDRA) with System Organ Classification (SOC) and reported with severity, duration, onset time and relationship to study drug and action taken.

Female subjects of child-bearing potential must have a negative pregnancy test at all visits where VFSS will be performed. Following administration of study drug, any known cases of pregnancy in female subjects will be reported until 30 days after the subject completes or withdraws from the study. The pregnancy will be reported immediately by phone and by faxing/emailing a completed Pregnancy Report to the Principal Investigator or study team within 24 hours of knowledge of the event. The pregnancy will not be processed as a serious adverse event (SAE); however the Principal Investigator will follow the subject until completion of the pregnancy and must assess the outcome in the shortest possible time but not more than 30 days after completion of pregnancy. If the outcome of the pregnancy meets the criteria for immediate classification of an SAE (e.g., spontaneous or therapeutic abortion [any congenital anomaly detected in an aborted fetus is to be documented] stillbirth, neonatal death, or congenital anomaly), the Principal Investigator will report the event by phone and by faxing a completed SAE form to the IRB and the FDA within 24 hours of knowledge of the event.

All serious adverse events (SAEs), whether or not the event is deemed drug-related, will be reported on the SAE Report Form

The Investigator will be responsible for notifying the IRB and regulatory agencies.

If a subject experiences a non-serious Adverse Event:

All clinical adverse events are recorded in the CRFs designed specifically for this purpose. It is important to report all AEs, especially those that result in permanent discontinuation of the investigational product being studied, whether serious or non-serious.

The site should fill out the CRF and enter the non-serious AE information into the online Adverse Event Reporting System within 5 working days/7 calendar days of the site learning of a new AE or receiving an update on an existing AE.

Expected adverse events for Metformin are provided in Section 6.4; *Safety*.

---

## **14. CRITERIA FOR INTERVENTION DISCONTINUATION**

Subjects will be discontinued from the study under the following circumstances:

- If the subject is hemodynamically unstable
- If discontinuation suspension is recommended by treating physician
- At the subject's request

## **15. STATISTICAL CONSIDERATIONS**

### **15.1. General Design Issues**

This open label study has been designed to assess the safety and tolerability of Metformin in individuals with C9orf72 positive ALS. The study will be performed at the University of Florida. The anticipated time from study enrollment until completion of data analyses is approximately 10-18 months. The inclusion criteria are intended to provide a cohort of subjects with ALS who are appropriate candidates for treatment with Metformin. Exclusion criteria prohibit enrollment of subjects with certain medical conditions, allergies to study drug or females that are pregnant or breastfeeding.

### **15.2. Outcomes**

#### **15.3. Primary and Secondary Outcomes:**

The primary objective of this study is to assess the safety and tolerability of Metformin administered twice daily.

Additional outcomes:

- Type, incidence, and severity of adverse events
- Physical and neurological examinations
- Vital signs (heart rate, blood pressure, respiration rate, temperature), Height/Weight
- Clinical laboratory tests (hematology, serum chemistry and urinalysis)
- BDI-Fast Screen
- Impact on swallowing
- Impact on respiratory testing
- Impact on RAN protein levels
- Impact on neuroimaging

---

#### **15.4. Sample Size and Accrual**

Using a conservative value, screening 50 individuals affected by ALS should yield the 16 study subjects for this protocol. Participants will be recruited from UF and multiple clinical sites in the state of Florida and throughout the US. Interested participants will be contacted by the investigators or their staff and invited to participate. These recruitment strategies will include a mechanism by which the subjects can provide their contact information.

#### **15.5. Data Monitoring**

Data Monitoring will be conducted according to Good Clinical Practice and applicable government regulations. The investigator agrees to allow monitors access to the clinical supplies, dispensing and storage areas, and the clinical files of the study subjects and, if requested, agrees to assist the monitors.

Safety monitoring will include careful assessment and appropriate reporting of adverse events. Medical monitoring will include contemporaneous assessment of serious adverse events.

#### **15.6. Data Analyses**

**15.7. Data analyses will be performed by the investigative team including individuals working in the [name] laboratory with the exception that [name] will not perform statistical analyses. General data analysis including impact on swallowing and respiration, and manuscript writing will also be performed by Co-Investigator [name] at Ohio State University.**

##### **Statistical Analysis**

Statistical analysis will be performed by investigators in the laboratories of Drs. [name], [name], [name] or [name]. Because [name] has a potential conflict of interest as an inventor of a pending patent and as a founder of RanTtran that may license this technology from UF in the future, she will not perform any of the specific statistical tests of the data generated during the course of this study. Summary statistics will be reported for safety and tolerability endpoints as listed above (Section 15.2.1) as well as subject characteristics (demographics, ALS Functional Rating Scale – Revised (ALSFRS-R), RAN protein levels, respiratory, and bulbar dysfunction).

Depending on the study enrollment rate, the PI may elect to perform an interim analysis using available data from the subset of subjects who have completed the study at that time. The results of this interim analysis will be used only for internal planning and possibly for sharing with regulatory authorities. The results of the interim analysis will have absolutely no influence on the subsequent conduct of the study.

---

##### **CONFIDENTIAL INFORMATION**

The information in this study protocol is confidential. Any disclosure, copying or distribution of the information contained within is strictly prohibited without written consent from University of Florida.

The Suicidal Ideation Score is a numerical score derived from the categories 1-7 on BDI-FastScreen (BDI-FS) present at the assessment. It will be reported as a numerical score and will be provided in the listing as well. If no ideation; then score is zero.

No formal statistical tests will be performed to compare Screening vs. Visit 1 vs Visit 2 vs Visit 3 on tolerability and safety endpoints.

Summary statistics will also include concomitant medications. No efficacy analysis will be performed.

Additional statistical and alternate tests may be performed, if necessary.

## **16. ETHICAL CONSIDERATIONS**

### **16.1. Basic Principles**

This research will be carried out in accordance with Good Clinical Practice (GCP) as set out by the International Council for Harmonization (ICH), the basic principles defined in the U.S. Code of Federal Regulations (21 CFR Part 312), the Belmont Report, Directive 2001/20/EC (Europe), The Tri-Council Policy Statement and the principles enunciated in the most recent version of the World Medical Association Declaration of Helsinki.

